### **4.5. Non-COVID-19 Impacted Population**

Non-COVID-19 Impacted Population will include all randomized subjects who do not have any COVID-19-related protocol deviations. The Non-COVID-19 Impacted population will be used for sensitivity analyses for the primary and secondary efficacy endpoints.

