## 3. SUMMARY OF STUDY DESIGN

This is a double-blind, randomized, placebo-controlled study evaluating the PK and safety of OCA in patients with PBC and moderate to severe hepatic impairment. It is a Phase 4 study in regions where OCA has received regulatory approval for PBC; in all other regions, this study is considered Phase 3b.

[figure not shown]
Approximately 50 patients (including at least 20% of patients with CP-C) will be enrolled in the study. Patients will be screened  $\geq 14$  days but not more than 28 days prior to entering the study (Day 1). Patients who meet all eligibility requirements will be randomized in a 1:1 ratio to 1 of 2 treatment groups: placebo or OCA. Randomization will be stratified by CP class. Baseline MELD scores will be monitored on an ongoing basis to ensure adequate distribution of MELD scores.

Patients will receive double-blind treatment for at least 48 weeks. During the 48-week treatment period (ie, Day 1 through Week 48), an initial safety visit will occur at Week 3. After the Week 6 Visit, subsequent clinic visits will occur approximately every 6 weeks for the assessment of safety, tolerability, PK, and PD. Titration may be considered as early as the Week 12 Visit. Fasting PK samples (ie, trough only) will be obtained from all patients on Day 1, Week 6, and Week 36 prior to dose administration. Post-dose serial PK assessments (including a trough sample) will be performed in all patients at Weeks 12, 18, 24, 30, and 48.

Patients who have completed their 48-week double-blind treatment period will continue double-blind treatment until all randomized patients have completed their participation in the 48-week treatment period and the database for that period is locked (approximately 3 years).

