### **4.2. Intent-to-Treat (ITT) Population**

The Intent-to-Treat (ITT) Population will include all randomized patients who received any amount of IP (OCA or placebo). The ITT Population will be the primary population used for summarizing efficacy and pharmacodynamic analyses assessments. Subjects will be analyzed according to randomized treatment.

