### 5.1. Protocol Deviations

The Investigator is not permitted to deviate from the protocol without proper notification to the Sponsor (or designee). Only the Sponsor may amend the protocol. Any change in study conduct considered necessary by the Investigator will be made only after consultation with the Sponsor, who will then issue a formal protocol amendment to implement the change and obtain regulatory approval. The only exception is when the Investigator considers a patient's safety to be compromised if immediate action is not taken.

Major protocol deviations that could potentially affect the efficacy or safety conclusions of the study will be identified prior to database lock and unblinding of individual subject treatment information. Major protocol deviations will be summarized by deviation category and treatment group for the ITT Population.

Protocol deviations related to COVID-19 are recorded in the Clinical trial management system as outlined within the Protocol Deviation and Non-Compliance Plan and will also be summarized by deviation category and treatment group.

Protocol deviations will be listed by subjects.

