## 9. EFFICACY ANALYSES

The efficacy endpoints of the study are defined below. Additionally, the planned analyses for these endpoints are described.

The efficacy analyses are additional endpoint in this study and will be performed on the ITT Population, as defined in [Section 4.2](#). Summary statistics will be tabulated for baseline, change and percent change from baseline to each scheduled visit of DB phase, Week 48 (end of DB phase), and each scheduled visit of DB extension (DBext) phase. An analysis of covariance (ANCOVA) model and Wilcoxon Rank Sum Test will be applied to the change and percent change from baseline to Week 48 and each scheduled visit of DB phase of efficacy parameters. All CIs for point estimates provided will be conducted using the two-sided 95% confidence intervals.

All efficacy data will be provided in listings by subject and visit.

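### The COVID-19 sensitivity population drops patients from the Week 48 analyses for deviations that occur only later, in the double-blind extension

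*SAP*

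**What the plan says.** SAP section 4.5 states that the Non-COVID-19 Impacted Population "will include all randomized subjects who do not have any COVID-19-related protocol deviations". On its use: "The Non-COVID-19 Impacted population will be used for sensitivity analyses for the primary and secondary efficacy endpoints". Nothing there restricts the deviation by date, visit, study phase, severity or relevance to the endpoint.

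Section 5.1 adds no restriction. It says "Protocol deviations related to COVID-19 are recorded in the Clinical trial management system as outlined within the Protocol Deviation and Non-Compliance Plan" and that these deviations will be summarized by category and treatment group.

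Section 4.2 sets the main analysis set: "The ITT Population will be the primary population used for summarizing efficacy and pharmacodynamic analyses assessments". Section 9 places the comparisons within the double-blind phase: the ANCOVA and Wilcoxon methods "will be applied to the change and percent change from baseline to Week 48 and each scheduled visit of DB phase". Descriptive summaries go further, to "Week 48 (end of DB phase), and each scheduled visit of DB extension (DBext) phase".

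Section 3 explains why follow-up runs past Week 48: patients who complete it "will continue double-blind treatment until all randomized patients have completed their participation in the 48-week treatment period" and until that period's database is locked, which the SAP puts at about three years.

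**The concern.** Exclusion is decided once per patient and over all time on study, whereas the comparisons stop at Week 48. An early enrollee may complete Week 48 with nothing affected and then have a COVID-19 deviation in the extension. Under section 4.5 that patient leaves the population, and all of the patient's double-blind data leave the sensitivity analysis.

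Two things are at stake. First, unaffected data are lost from an analysis that starts with only about 25 patients per arm. Second, the chance of being excluded grows with the number of visits at which a deviation can occur, so patients who enrolled early and stayed on study are more likely to be removed. A change from the ITT estimate may then partly reflect a different mix of patients rather than the removal of affected assessments.

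**Working it through.** **Timing, from the text.** Section 4.5 counts a deviation at any time. Section 9 compares the arms at visits up to Week 48. Section 3 continues treatment after that. A deviation dated after a patient's Week 48 visit cannot have changed a value recorded at or before it, yet it triggers exclusion. Section 5.1 does not repair this. The authors did use a relevance filter elsewhere: section 4.4 removes patients from the PK Population only for major deviations that could affect exposure.

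**Size, as an illustration.** The SAP states no figure for this loss, so there is none to reproduce.

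Inputs from the SAP:
- N is about 50, randomized 1:1 (section 3.3; its components 20 + 10 + 20 = 50 agree).
- Post-baseline double-blind visits: Week 3, Week 6, then "After the Week 6 Visit, subsequent clinic visits will occur approximately every 6 weeks". This gives Weeks 3, 6, 12, 18, 24, 30, 36, 42 and 48, which is 9 visits.

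Assumed, because the SAP gives no value: deviation risk p per visit from 1% to 10%; m extension visits from 0 to 16; independence between visits; no dropout.

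Formulas:
- Kept under section 4.5: 50 × (1 − p)^(9 + m)
- Kept if only deviations up to Week 48 count: 50 × (1 − p)^9
- Share excluded for extension deviations alone: (1 − p)^9 − (1 − p)^(9 + m)
- Standard-error ratio due to that share: (1 − p)^(−m/2), the square root of the ratio of patients kept, assuming the same SD and balanced loss

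With m = 8:

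| p | Kept, section 4.5 | Kept, up to Week 48 | Excluded for extension only | SE increase |
|---|---|---|---|---|
| 1% | 42.1 | 45.7 | 7.1 points | 4% |
| 2% | 35.5 | 41.7 | 12.4 points | 8% |
| 5% | 20.9 | 31.5 | 21.2 points | 23% |
| 10% | 8.3 | 19.4 | 22.1 points | 52% |

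With p = 2% and other values of m:
- m = 0: 41.7 kept under either rule, so no loss.
- m = 4: 38.5 kept, 6.5 points, SE up 4%.
- m = 16: 30.2 kept, 23.0 points, SE up 18%.

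**Dependence on follow-up.** At p = 2%, a patient who completes Week 48 with no extension visit stays in with probability 0.98^9 = 83.4%. One with 16 extension visits stays in with probability 0.98^25 = 60.3%. Both have the same 9 double-blind visits. If only deviations up to Week 48 counted, both would have 83.4%.

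**The case against.** The stakes are limited. The population serves sensitivity analyses only. The ITT analysis keeps every treated patient, section 2.2 states no formal hypothesis, the primary objectives are PK and safety, and section 9 calls efficacy an additional endpoint. Excluding whole patients is blunt but transparent. What counts as a COVID-19 deviation is set in a separate plan, and deviations after the data cut for the 48-week lock may never enter the determination. Extension deviations are also relevant to the descriptive extension summaries. All of this stands. It limits the weight of the point but leaves the mismatch in timing, because extension deviations of early enrollees before that cut would still count.

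A reader might infer more than the SAP supports:
- *That Week 48 data are lost to the trial.* They are lost only to this sensitivity analysis.
- *That COVID-19 altered ascertainment part-way through.* The SAP gives no enrolment dates, missed-visit counts or record of remote assessments.
- *That about half of exclusions would be needless.* If 156 weeks run from first patient to lock and accrual is uniform over the first 108, the mean extension is 54 weeks, and 54/(48 + 54) = 53% of patient time falls after Week 48. That is a share of time, not of patients. It ignores dropout and needs deviations to be spread evenly over time. The SAP's three years could also mean the length of continued treatment.
- *That standard errors rise by 12% to 41%.* Keeping 40 or 25 of 50 gives √(50/40) = 1.12 and √(50/25) = 1.41, but this charges every exclusion to the flaw, including those for deviations before Week 48, and the rates are assumed.
- *That a difference from ITT could never be put down to COVID-19.* This is too absolute. Treatment stays blinded in the extension, and nothing in the SAP suggests that deviations differ by arm. The difference is harder to interpret, not uninterpretable.

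**Conclusion.** The point holds for the sensitivity analysis and no further. As written, section 4.5 lets a deviation after Week 48 remove a patient whose data through Week 48 it cannot have affected. This reduces precision without need and ties membership to length of follow-up. ITT results are untouched.

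The actual loss is unknown, because the SAP gives neither a deviation rate nor the number of extension visits. The tabulated figures depend on those assumptions and on independence between visits, and they run from no loss to a large one. The conclusion about timing needs none of these assumptions; it rests on section 4.5 meaning what it says, since that section does not name the extension. The correction is worth making because it costs almost nothing.

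**What to change.** Reword section 4.5 so that, for double-blind-phase and Week 48 analyses, a patient is excluded only for a COVID-19 deviation dated on or before the analysed visit, and at the latest Week 48. A model that uses all double-blind visits together, such as the MMRM, can take Week 48 as its single cut-off. Extension deviations should count only for extension summaries. State that membership is determined before unblinding.

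As an optional supplement, keep all ITT patients and set only the COVID-19-affected assessments to missing. The planned MMRM can then use the remaining visits for liver biochemistry, TE and ELF. MELD, Child-Pugh, bile acids, C4 and FGF-19 are planned with Wilcoxon tests, which would use the available cases at each visit and cannot borrow from other visits. This supplement is a choice with trade-offs and should not replace the main correction.

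The cost is a short change of wording and minor programming to link deviation dates to visits. The deviations are already recorded in the trial management system, and section 1 has the SAP finalized before database lock.

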## 5. SUBJECT DISPOSITION

Subject disposition will be tabulated by treatment group and overall and will include the number and proportion of subjects:

- Enrolled
- Randomized
- Randomized but not treated
- ITT Population
- Safety Population
- PK Population
- Non-COVID-19 Impacted Population
- Subjects who completed the study, withdrew from the study and the reasons for the withdrawal
- Subjects who completed the study treatment, withdrew from the study treatment and reasons for the withdrawal
- Subjects who completed Week 48 Visit of double-blind (DB) phase
- Subjects' study status post study treatment as recorded on the eCRF.

Proportions will be out of the number of randomized subjects.

Similar disposition summary will be done also other ITT, Safety, PK and Non-COVID-19 impacted population. Proportions will be out of the number of subjects in the given population.

Subjects' completion/discontinuation status will be listed including subject identifier, informed consent date, treatment completion, date of last treatment, dose regimen at date of last treatment, reason for treatment discontinuation, study completion, date of study completion or early withdrawal, and reason for study discontinuation.

### 5.1. Protocol Deviations

The Investigator is not permitted to deviate from the protocol without proper notification to the Sponsor (or designee). Only the Sponsor may amend the protocol. Any change in study conduct considered necessary by the Investigator will be made only after consultation with the Sponsor, who will then issue a formal protocol amendment to implement the change and obtain regulatory approval. The only exception is when the Investigator considers a patient's safety to be compromised if immediate action is not taken.

Major protocol deviations that could potentially affect the efficacy or safety conclusions of the study will be identified prior to database lock and unblinding of individual subject treatment information. Major protocol deviations will be summarized by deviation category and treatment group for the ITT Population.

Protocol deviations related to COVID-19 are recorded in the Clinical trial management system as outlined within the Protocol Deviation and Non-Compliance Plan and will also be summarized by deviation category and treatment group.

Protocol deviations will be listed by subjects.

## 5.2. Inclusion/Exclusion Criteria

Inclusion/exclusion criteria definitions and violations will be listed. If no inclusion/exclusion violations are reported, this will be noted in place of the listing.

## 6. DEMOGRAPHICS AND BASELINE DISEASE CHARACTERISTICS

Demographics and baseline characteristics will be summarized and presented by treatment group and overall for ITT, Safety, and PK Populations.

Age (years), height (cm), weight (kg), body mass index (BMI) (kg/m^2), baseline CP score and baseline CP class (Class B/Class C), baseline MELD score, and Rotterdam criteria at baseline will be summarized descriptively. Summary statistics will include the number of subjects and the mean, standard deviation (SD), standard error of the mean (SE), median, 25th and 75th quartiles, minimum, and maximum values. Key liver function test results including ALP, total bilirubin, INR, platelets, albumin, Total daily dose of UDCA (mg) at baseline, Time from first initiated UDCA to first dose (weeks), and Time from last date of highest UDCA use to first dose (weeks) will also be summarized descriptively.

Sex, Race, Ethnicity, and Use of UDCA (Yes/No) will be summarized by frequency counts and percentages. A subject can have multiple races and will be summarized as Multiple Races. A subject can also have multiple ethnicities and will be summarized as Multiple Ethnicities.

BMI is calculated based on weight and height at baseline.

Demographic data and baseline characteristics (as detailed above) as well as informed consent data will be listed.

- Age (in years) is derived by IWRS as year of screening minus year of birth
- Height (in cm) = height (in inches) \* 2.54
- Weight (in kg) = weight (in lbs) \* 0.4536
- BMI (kg/m^2) = Weight(kg)/[Height(cm)/100]
- Total daily dose of UDCA (mg) at baseline is determined as the last dosage reported prior to the first dose.
- Time from first initiated UDCA to first dose (weeks) = (first dose date – date of first initiated UDCA)/7
- Time from last date of highest UDCA use to first dose (weeks) = (first dose date - date of highest UDCA)/7

- Rotterdam criteria (Kuiper 2009) at baseline is defined as:
  - Low = Total Bilirubin< ULN and Albumin>LLN
  - Moderate = Total Bilirubin<ULN and Albumin<LLN or Total Bilirubin>ULN and Albumin>LLN
  - High = Total Bilirubin>ULN and Albumin<LLN

Demographics and baseline characteristics will be listed by subject.

## **7. PBC DISEASE HISTORY**

PBC disease history will be summarized and presented by treatment group and overall for ITT, Safety, and PK Populations. The number and percentage of subjects in each of the following categories will be presented.

- Age at PBC diagnosis
- Duration of PBC in years at time of informed consent
- Time in years from PBC Diagnosis to first dose of UDCA
- History of PBC related pruritus (Yes/No)
- Severity of most recent pruritus event
- Pruritus ongoing at time of screening (Yes/No)

## **8. PRIOR THERAPY AND MEDICAL HISTORY**

Prior therapy and medical history are any therapy, procedures, or diseases that occurred, or any medication taken prior to the first day of study drug dosing or prior to randomization date if subjects were never dosed.

Medical history will be mapped to preferred terms and system organ classes using MedDRA dictionary version 24.0 and summarized by system organ class, preferred term, and treatment group and overall using the Safety population. Summaries will be ordered by descending order of incidence of system organ class and preferred term within each system organ class.

A listing of medical history by subject will be provided. A listing of cirrhosis status assessment by subject will also be provided.

Historical procedures will be coded with MedDRA version 24.0. A summary of historical procedures will be presented by MedDRA SOC, PT, and by treatment group and overall using the Safety Population. A listing of historical procedures by subject will be provided.

## 9. EFFICACY ANALYSES

The efficacy endpoints of the study are defined below. Additionally, the planned analyses for these endpoints are described.

The efficacy analyses are additional endpoint in this study and will be performed on the ITT Population, as defined in [Section 4.2](#). Summary statistics will be tabulated for baseline, change and percent change from baseline to each scheduled visit of DB phase, Week 48 (end of DB phase), and each scheduled visit of DB extension (DBext) phase. An analysis of covariance (ANCOVA) model and Wilcoxon Rank Sum Test will be applied to the change and percent change from baseline to Week 48 and each scheduled visit of DB phase of efficacy parameters. All CIs for point estimates provided will be conducted using the two-sided 95% confidence intervals.

All efficacy data will be provided in listings by subject and visit.

### 9.1. MELD Score

MELD score is derived from the patient's serum total bilirubin, serum creatinine, and INR, as appropriate, to predict survival ([Kamath 2007](#)). MELD score will be calculated and reported for visits where these parameters are measured as described in the protocol. An increasing MELD score is associated with increased severity of hepatic dysfunction and increased 3-month mortality risk.

- Summary statistics of MELD score including baseline values, change from baseline, and Percentage change from baseline values will be presented by treatment group and by each scheduled post-baseline visit.
- Analysis of change from baseline in MELD score will be analyzed using the Wilcoxon Rank Sum Test. The tabulation will include median, interquartile range for each treatment group, median differences and 95% CI of the median differences between treatment groups using the Hodges-Lehmann estimate. If the median differences between treatments are not symmetrical around the median, the Sign Test may be used.
- MELD score will be presented in shift tables showing the shift from baseline to each scheduled post-baseline visit by the count and percentage of patients within each shift classification (<10, 10 to <12, 12 to <13, 13 to <14, 14 to <15, and  $\geq 15$ ).

The MELD Score analyses will be repeated for MELD-Na

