### **3.2. Randomization and Blinding**

This study will be conducted in a double-blind, placebo-controlled manner. Enrolled patients who meet all eligibility requirements will be randomized in a 1:1 ratio to 1 of 2 treatment groups: placebo or OCA based on a predefined randomization code (generated by Sponsor or designee) using an interactive web response system (IWRS), which the Sponsor intends will serve as a computer-based patient registration system at Screening and Day 1.

Randomization will be stratified by CP class (CP-B or CP-C). Baseline MELD scores will be monitored on an ongoing basis to ensure adequate distribution of MELD scores. The IWRS will serve as the IP inventory and management system and may be integrated with the study database.

The Investigator or designee will be required to register the patient in the IWRS and may be prompted to provide patient data necessary to properly randomize and allocate the patient to treatment. A randomization number will be assigned and IP (placebo or OCA) dispensing information will be provided (eg, bottle numbers allocated) while maintaining the study blind.

The sponsors, patients, investigators, and study site staff will be blinded to the patient's treatment allocation during the patient's participation in the double-blind phase of the study.

Treatment assignment for individual patients will be made available to the Investigator for medical emergency use only (such as unblinding which is necessary in order to treat a serious adverse event through the IWRS system). When possible, the Medical Monitor should be consulted in the event that a medical emergency necessitates unblinding (ie, in situations where knowledge of the blinded treatment assignment is necessary for further medical management of the patient). If it is not reasonable to inform the Medical Monitor in advance of the unblinding, the Investigator must promptly document in the patient's record the rationale for unblinding and should subsequently contact the Medical Monitor to explain any premature unblinding of treatment assignment. Procedures for unblinding a patient's treatment will be provided separately to the Investigator. Similarly, if the Medical Monitor breaks the blind for an individual patient for the purpose of evaluating an emergent safety issue, the Medical Monitor will document within study documentation the rationale, circumstances, and the person or persons being informed about the unblinding.

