**Table 2: Child-Pugh Scoring System**

Factor	Units	Points		
		1	2	3
Serum bilirubin	µmol/L	<34	34-50	>50
	mg/dL	<2.0	2.0-3.0	>3.0
Serum albumin	g/L	>35	28-35	<28
	g/dL	>3.5	2.8-3.5	<2.8
Prothrombin time	Seconds prolonged	0-3	4-6	>6
	INR	<1.7	1.7-2.3	>2.3
Ascites		None	Mild	Moderate-Severe
Hepatic encephalopathy a		0	Grade 1 or 2	Grade 3 or 4

a Grade 0: normal consciousness, personality, neurological examination, electroencephalogram  
 Grade 1: restless, sleep disturbed, irritable/agitated, tremor, impaired handwriting, 5 cps waves  
 Grade 2: lethargic, time-disoriented, inappropriate, asterixis, ataxia, slow triphasic waves  
 Grade 3: somnolent, stuporous, place-disoriented, hyperactive reflexes, rigidity, slower waves  
 Grade 4: unrousable coma, no personality/behavior, decerebrate, slow 2-3 cps delta activity  
 (Pugh 1973, Lucey 1997), Vilstrup 2014

- Baseline CP score is calculated based on components measured at Screening visit.
- Summary statistics of CP score including baseline values, change from baseline, and percentage change from baseline values will be presented by treatment group and by each scheduled post-baseline visit.
- Analysis of change from baseline in CP score will be analyzed using the Wilcoxon Rank Sum Test. The median differences and 95% CI of the median differences between treatment groups will be constructed using the Hodges-Lehmann estimate. If the median differences between treatments are not symmetrical around the median, the Sign Test may be used.
- CP class (A, B, and C) will be presented in a shift table showing the shift from baseline to each scheduled post-baseline visit by the count and percentage of patients within each shift classification (A, B, and C).
- Components of CP score categories as listed in Table 2 will be summarized by the count and percentage of patients within each category at baseline and each scheduled post-baseline visit.

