### 9.3. Liver Biochemistry and Hepatobiliary Damage

Liver biochemistry includes total and direct bilirubin, ALP, ALT, AST, and GGT, INR, creatinine, albumin, and platelets.

- Summary statistics of liver biochemistry including baseline values, change from baseline, and percentage change from baseline values will be provided by treatment group and by each scheduled post-baseline visit.
- Change from baseline will be analyzed by using an ANCOVA model with change from baseline as the dependent variable, treatment group and randomization stratification factor as fixed effects and the baseline value as a covariate.
- Percent change from baseline will be analyzed by using an ANCOVA model with percent change from baseline as the dependent variable, treatment group and randomization stratification factor as fixed effects and the baseline value as a covariate.
- As a sensitivity analysis, change from baseline and percent change from baseline of liver biochemistry parameters will be analyzed by using a restricted maximum likelihood (REML) based MMRM. Treatment group, time, treatment group by time interaction, and randomization stratification factor will be included as fixed effects and parameter baseline values will be included as a covariate in the model, where time includes all post baseline visits of DB phase.
- An unstructured covariance structure will be used to model the within-participant errors. If there is a convergence issue with the unstructured covariance model, Toeplitz, Autoregressive (1) (AR (1)) covariance structure will be used, following this sequence until convergence is achieved. If the model still does not converge with AR (1) structure, no results will be reported. When the covariance structure is not unstructured, the sandwich estimator for the variance-covariance matrix will be derived, using the EMPIRICAL option in the PROC MIXED statement in SAS. The p-value will be interpreted at 0.05 level of significance.
- The tabulation of ANCOVA model and MMRM model will include estimates of least-square (LS) means, SEs, and 2-sided 95% CIs for each treatment group. Estimates of the mean difference, SE of the difference, 2-sided 95% CI of the difference between treatment groups, and p-value will also be presented.

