### 9.4. Total Bile Acids, Total Endogenous Bile Acids, C4 and FGF-19 Concentrations

Total bile acids, total endogenous bile acids, C4 and FGF-19 concentrations will be analyzed as follows:

- Summary statistics of total bile acids, total endogenous bile acids, C4 and FGF-19 concentrations including baseline values, change from baseline, and percentage change from baseline values will be presented by treatment group and by each scheduled post-baseline visit.

- Change from baseline in total bile acids, total endogenous bile acids, C4 and FGF-19 concentrations at each scheduled post-baseline visit will be analyzed using the Wilcoxon Rank Sum Test.

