### **Missing Data**

All available data of the subjects who withdraw from the study for any reasons will be analyzed. Missing data will be assumed to be missing at random. There will be no imputation of missing data for the analysis purpose. Change from baseline of an endpoint will be missing when either baseline value of the endpoint is missing or post-baseline value of the endpoint is missing.

Incomplete start and end dates for adverse events and concomitant medications are imputed as follows:

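### The rank tests for MELD, Child-Pugh, bile acids, C4 and FGF-19 leave out the randomization stratum, and the MELD and CP comparisons have no rule for visits after death or transplant

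*SAP*

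**What the plan says.** **Design.** SAP Section 3.2: "Randomization will be stratified by CP class (CP-B or CP-C"). Section 3.3 plans about 50 patients, allocated 1:1, at least 20% of them CP-C.

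**Rank tests.** Section 9.1: "Analysis of change from baseline in MELD score will be analyzed using the Wilcoxon Rank Sum Test". It adds a Hodges-Lehmann difference with 95% CI, and repeats the analyses for MELD-Na. Section 9.2: "Analysis of change from baseline in CP score will be analyzed using the Wilcoxon Rank Sum Test". Section 9.4, for total and endogenous bile acids, C4 and FGF-19: change "at each scheduled post-baseline visit will be analyzed using the Wilcoxon Rank Sum Test". No stratum is named in any of the three.

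**Other models.** The ANCOVA in Sections 9.3 and 9.5 has "treatment group and randomization stratification factor as fixed effects and the baseline value as a covariate". The MMRM also includes the factor, and the log-rank test and Cox model in Section 9.6 are stratified by it.

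**General statement.** The opening of Section 9 says: "An analysis of covariance (ANCOVA) model and Wilcoxon Rank Sum Test will be applied to the change and percent change from baseline to Week 48". The same sentence covers the other double-blind visits too. Sections 9.1, 9.2 and 9.4 then give only the rank test.

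**Missing data.** Appendix A: "Missing data will be assumed to be missing at random". It allows no imputation, sets a change score to missing when the visit value is missing, and analyses whatever data exist for patients who withdraw. It has no rule for visits after death or liver transplant.

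**The concern.** Stratified randomization balances CP class between arms, so differences in change between the classes cannot produce a difference between arms. An unstratified rank-sum test still counts that between-class spread as noise. Its true error rate then falls below 5%, and it gives up precision the design has already provided. The rest of the SAP uses the stratum, and Section 12.3.3 even tabulates the same bile acid, C4 and FGF-19 data by CP category.

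The second issue is separate. Section 9.1 itself links a rising MELD score to higher 3-month mortality. A patient who dies therefore goes missing because of the process MELD measures, and missing at random is hard to defend. A visit-by-visit rank test also uses no earlier post-baseline values, so it would not be protected even if that assumption held. The MMRM sensitivity analysis covers only the parameters of Sections 9.3 and 9.5, and the Non-COVID-19 population does not address death. MELD and CP thus have no missing-data sensitivity analysis. If one arm loses more of its worsening patients, its survivors look better on both scores.

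**Working it through.** **The plan's own figures.** 20 OCA + 10 placebo + 20 additional = 50, or 25 per arm. The CP-C minimum is 0.20 × 50 = 10, or 5 per arm. The 20 on OCA comes from a PK simulation whose inputs are not given, and Section 2.2 sets no formal hypothesis. There is therefore no stated power to reproduce for these tests, and every effect size, class shift and event rate below is an assumption.

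**Yardstick.** Normal approximation for 0.8 SD, 25 per arm, two-sided 5%: Φ(0.8 × √(25/2) − 1.96) = Φ(0.868) = 80.7%.

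**Part 1: the stratum.** In stratum k with N_k patients, let W_k be the rank sum in the OCA arm, E_k = n_1k(N_k+1)/2, and V_k = n_1k·n_0k(N_k+1)/12 without ties.

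- Rank-sum: z = (W − E)/√V over all 50 patients.
- Van Elteren: z = Σw_k(W_k − E_k)/√(Σw_k²V_k), with w_k = 1/(N_k+1). Here that is 1/41 for CP-B and 1/11 for CP-C.

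Results of 40,000 simulations with normal change scores and 5 CP-C per arm:

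| CP-C shift in change | Size, rank-sum | Size, van Elteren | Power, rank-sum | Power, van Elteren | Loss (points) |
|---|---|---|---|---|---|
| 0 SD | 5.0% | 5.0% | 76.8% | 76.1% | −0.7 |
| 0.5 SD | 4.5% | 5.0% | 76.1% | 76.3% | 0.2 |
| 1 SD | 3.6% | 5.1% | 72.0% | 76.2% | 4.2 |
| 1.5 SD | 2.3% | 4.8% | 66.1% | 76.2% | 10.1 |
| 2 SD | 1.6% | 5.0% | 58.7% | 76.4% | 17.7 |

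Hand check at 1 SD: between-class variance is 0.2 × 0.8 × 1² = 0.16, so the pooled variance is 1.16. The effective critical value is 1.96 × √1.16 = 2.11, a size of about 3.5%, close to the simulated 3.6%. A repeat with 20,000 runs gave power of 76.5 v 75.6% at 0 SD, 72.0 v 76.0% at 1 SD and 58.8 v 76.2% at 2 SD. With 12 CP-C per arm the loss is larger: 74.6 v 75.8% at 0.5 SD and 68.5 v 76.3% at 1 SD.

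**Part 2: deaths.** 25 per arm, higher change is worse, 6,000 runs per scenario. An event occurs when a latent severity exceeds its cut-off. In the linked scenarios that severity has correlation 0.7 with the patient's change. Event patients are either dropped or all given the worst rank.

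| Events, placebo v OCA | Linked to worsening? | True harm | Mean estimate, dropped | Harm detected, dropped | Harm detected, worst rank |
|---|---|---|---|---|---|
| 8% v 8% | yes | 0.5 SD | 0.50 | 38.8% | 31.8% |
| 8% v 16% | yes | 0.5 SD | 0.41 | 28.5% | 38.4% |
| 8% v 24% | yes | 0.5 SD | 0.33 | 19.7% | 45.1% |
| 8% v 24% | no | 0.5 SD | 0.50 | 32.8% | 59.4% |
| 8% v 24% | yes | 0 | −0.18 | 0.6% | 6.9% |

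In the last row, dropping gives a significant result in OCA's favour in 9.0% of runs, against a nominal 2.5%. The bias needs both imbalance and linkage: it vanishes when either is absent. The worst-rank figures partly reflect the excess events themselves, so they answer a composite question and not a cleaner version of the same one.

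**The case against.** **No power is promised.** There is no formal hypothesis, the sample size comes from PK, and Section 9 calls efficacy additional. That stands: nothing stated is eroded, and a conservative test is not an invalid one. The SAP still plans these tests with p-values or intervals, so they should match the design.

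**The loss may be nil.** A change score already subtracts each patient's baseline, and nothing in the SAP shows that class shifts change by 1 SD. This also stands. The case for stratifying is that it costs under 1 point if class does not matter and recovers 4 to 18 points if the shift is 1 to 2 SD.

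**ANCOVA may already be planned.** The opening of Section 9 can be read that way. Sections 9.1, 9.2 and 9.4 do not carry it through, and the general sentence names no stratum, so this is at best an ambiguity.

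**Three stronger readings are tempting and not supported.**

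- A reader might infer that transplanted patients are dropped. No section says so. Because all data that exist are analysed, post-transplant values, if collected, would enter and could count as improvement.
- A reader might infer that harm is hidden. Death, liver-related death, transplant and their composite have stratified analyses in Section 9.6. Transplant and a persistent 3-point MELD rise are events of special interest in Section 10.3.3, and AEs leading to death are listed. Only the MELD and CP comparisons could mislead.
- A reader might infer that the rank tests cover most secondary endpoints. By count they cover seven variables: MELD, MELD-Na, CP, two bile acid totals, C4 and FGF-19. Ten liver biochemistry parameters have stratum-adjusted ANCOVA and MMRM. Those include bilirubin, INR and creatinine, from which MELD is built.

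**Conclusion.** The point holds in two limited parts.

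1. The rank tests in Sections 9.1, 9.2 and 9.4 omit the stratum that the design and the SAP's other models use. The result is a valid but conservative test. The loss is negligible up to a 0.5 SD class shift, then about 4, 10 and 17 to 18 points at 1, 1.5 and 2 SD. This assumes a 0.8 SD effect, normal change scores and 5 CP-C patients per arm.
2. Deaths leave later MELD and CP comparisons, and post-transplant handling is unstated. If events are unbalanced and linked to worsening, the comparison shifts toward the arm with more events. The shift is about 0.17 to 0.18 SD at an assumed 8% v 24%, and zero when rates are equal or events are unrelated to change.

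These are secondary endpoints. The primary PK and safety aims and the separate analyses of death and transplant are not affected.

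**What to change.** - In Sections 9.1, 9.2 and 9.4, replace the rank-sum test with a van Elteren test stratified by randomized CP class, and report a stratified Hodges-Lehmann estimate and 95% CI.
- For MELD, MELD-Na and CP only, add a sensitivity analysis using the same test, with death or liver transplant before the visit ranked worst and death worst of all. Post-transplant values then cannot count as improvement. Do not extend this to bile acids, C4 or FGF-19, where a worst rank is harder to justify.
- State in Appendix A whether post-transplant values enter the main MELD and CP tests.
- Align the opening of Section 9 with its subsections by saying which parameters get ANCOVA.

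**Cost.** SAP wording and a few lines of code, before the SAP is finalized ahead of database lock. Up to about 1 point of power is lost if class does not predict change, and the CP-C stratum may hold only about 5 patients per arm. The worst-rank result has no estimate in score units, and it loses power when event rates are balanced (31.8 v 38.8% above). It should therefore supplement the main test and not replace it.
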